4.8.6 Interim Analysis

One interim analysis is planned after all subjects have completed the 90 days post dose safety follow-up. This interim analysis will provide safety and immunogenicity data needed to select an antigen dose to include in the Phase 1b study, which will explore single ascending adjuvant doses in combination with the selected dose of RSV sF. Interim safety and safety laboratory data will be monitored and cleaned but not locked to permit incorporation of any safety data that the sites become aware of subsequently into the Day 1 through 90 safety evaluations. Unblinding for this interim analysis is described in Section 4.6.3.2.

Immunogenicity data that will be included in this interim analysis will be the results of the RSV A microneutralization assay; anti-F IgG assay derived from RSV-specific 4-plex MSD assay; and RSV F peptide pool IFN γ ELISPOT assay. In addition, wild-type RSV infection will be detected by anti-Ga, anti-Gb, or anti-N IgG assays derived from the RSV-specific 4-plex MSD assay to exclude subjects who have had wild-type RSV infections from the immunogenicity cohort.

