4.6.2 Methods for Ensuring Blinding

This is a double-blind study. Cohort allocation is not blinded, but treatment allocation within each cohort is blinded. Initially, subjects, investigators, blinded site staff, and MedImmune staff, including laboratory and site staff, are blinded. Subjects, investigators, and blinded site staff will remain blinded until the end of the study; however, MedImmune staff will be unblinded after Day 90 safety data have been cleaned and monitored and final immunogenicity data through Day 28 have been recorded as described in Section 4.8.6 (Interim Analysis).

In this double-blind study, RSV sF, MEDI7510, and placebo are not identical in appearance. Neither the subject nor any of the investigator or sponsor staff who are involved in the treatment or clinical evaluation of the subjects will be aware of the treatment received (International Conference on Harmonisation [ICH] E9; see Section 4.6.3.2 for unblinding related to interim analysis). Because RSV sF, MEDI7510, and placebo are not identical in appearance, investigational product will be handled by an unblinded investigational product manager at the site in accordance with the dosing cohorts of antigen alone and antigen plus adjuvant. An independent investigational product monitor, who may be the research pharmacist, will also be unblinded to perform investigational product accountability. Both investigational product and placebo will be drawn up by the unblinded pharmacist into a syringe that is subsequently blinded with a covered bore, such that vaccine contents are not visible, and provided to a blinded staff member for IM dosing. Thus, RSV sF and its placebo and MEDI7510 and its placebo will be identically labeled and indistinguishable in appearance when brought to the clinic. Refer to Appendix 5 (Mixing and Administration Instructions for RSV sF, MEDI7510, and Placebo) for blinding instructions.

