4.6.3.2 Unblinding for Interim Analysis Purposes

An interim analysis is planned for this study as described in Section 4.8.6. For this analysis and any ad hoc analysis that may occur between interim analysis and study completion MedImmune employees and the ESMC will be fully unblinded to all safety and immunogenicity data for data analysis purposes once all subjects complete the Day 91 visit. The subjects, the clinical research organizations that are responsible for site management and laboratory assay performance, and all site staff will remain blinded. Additional details will be documented in a separate unblinding plan.

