5.7.4 Adverse Events of Special Interest for an Adjuvanted Vaccine

Adverse events of special interest for an adjuvanted vaccine include the following verbatim terms and, for analysis, will also include associated MedDRA terms. Events that are faxed in by investigators as potential AESIs for an adjuvanted vaccine that do not meet these criteria will not be analyzed as AESIs.

- Neuroinflammatory disorders:
 - Optic neuritis
 - Uveitis
 - Multiple sclerosis
 - Demyelinating disease
 - Transverse myelitis
 - Guillain-Barré syndrome
 - Myasthenia gravis
 - Encephalitis
 - ADEM (acute disseminated encephalomyelitis)
 - Neuritis
 - Bell’s Palsy
- Musculoskeletal and connective tissue disorders:
 - Rheumatoid arthritis
 - Juvenile rheumatoid arthritis
 - Polymyalgia rheumatica
 - Psoriatic arthropathy
 - Ankylosing spondylitis
 - Spondyloarthropathy
 - Systemic lupus erythematosus
 - Cutaneous lupus

- Sjogren's syndrome
- Scleroderma
- Dermatomyositis
- Polymyositis
- Mixed connective tissue disease
- Vasculitides:
 - Vasculitis
 - Temporal arteritis
 - Wegener's granulomatosis
 - Behçet's syndrome
- Gastrointestinal disorders:
 - Crohn's disease
 - Ulcerative colitis
 - Inflammatory bowel disease (non-specific)
 - Celiac disease
 - Autoimmune hepatitis
 - Primary sclerosing cholangitis
 - Primary biliary cirrhosis
- Renal disorders:
 - Glomerulonephritis
 - Nephritis
- Cardiac disorders:
 - Carditis
 - Pericarditis
 - Myocarditis
- Skin disorders:
 - Psoriasis
 - Vitiligo
 - Raynaud's phenomenon
 - Erythema nodosum
 - Autoimmune bullous skin diseases
 - Stevens-Johnson syndrome
- Hematologic disorders:
 - Autoimmune hemolytic anemia
 - Idiopathic thrombocytopenic purpura
 - Antiphospholipid syndrome
- Metabolic disorders:

- Autoimmune thyroiditis
- Grave's disease (or its synonym, Basedow's disease)
- Hashimoto's thyroiditis
- Insulin-dependent diabetes mellitus
- Addison's disease
- Other disorders:
 - Sarcoidosis

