6.2 Monitoring of the Study

During the study, a MedImmune representative will have regular contact with the study site, including visits to:

- Provide information and support to the investigator(s)
- Confirm that facilities remain acceptable
- Confirm that the investigational team is adhering to the protocol, that data are being recorded in the eCRFs in an accurate and timely manner, that biological samples are handled in accordance with the Laboratory Manual and that investigational product accountability checks are being performed
- Perform source data verification (a comparison of the data in the eCRFs with the subject's medical records at the hospital or practice, and other records relevant to the study) including verification of informed consent of participating subjects. This will require direct access to all original records for each subject (eg, clinic charts)
- Ensure that withdrawal of informed consent for the use of the subject's biological samples is reported and biological samples are identified and disposed of/destroyed accordingly, and the action is documented, and reported to the subject

The MedImmune representative will be available between visits if the investigator(s) or other staff at the center needs information and advice about the study conduct.

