6.4 Data Management

Data management will be performed by MedImmune Data Management according to the Data Management Plan.

A Web Based Data Capture (WBDC) system will be used for data collection and query handling. The investigator will ensure that data are recorded on the eCRFs as specified in the study protocol and in accordance with the instructions provided.

The investigator ensures the accuracy, completeness, and timeliness of the data recorded and of the provision of answers to data queries according to the Clinical Study Agreement. The investigator will sign the completed eCRFs. A copy of the completed eCRFs will be archived at the study sites.

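### After the interim, sponsor staff as a whole may know the allocation while Day 1 to 90 safety data stay unlocked, and no rule keeps them from queries, coding, event classification or site contact

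*Protocol*

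**What the plan says.** Who is unblinded: Protocol Section 4.6.3.2 states that "MedImmune employees and the ESMC will be fully unblinded to all safety and immunogenicity data for data analysis purposes", with the timing "once all subjects complete the Day 91 visit". This covers the interim and any ad hoc analysis up to study completion. Subjects, site staff and the CROs for site management and assay performance stay blinded. Further detail is left to a separate unblinding plan.

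When: Section 4.6.2 words the trigger differently: "MedImmune staff will be unblinded after Day 90 safety data have been cleaned and monitored", and after the immunogenicity results through Day 28 are final.

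State of the data: Section 4.8.6 says "Interim safety and safety laboratory data will be monitored and cleaned but not locked to permit incorporation of any safety data" that sites learn of later. The only lock in the protocol comes before the final analysis (Section 4.8.7).

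Who handles the data: Section 6.4 says "Data management will be performed by MedImmune Data Management", using a web-based system for collection and queries. The investigator is responsible for the entries and signs the eCRFs. Under Section 6.2, "a MedImmune representative will have regular contact with the study site", including source data verification.

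Where judgment enters: Section 5.7.4 lists the AESI terms, adds associated MedDRA terms, and says that events faxed in "that do not meet these criteria will not be analyzed as AESIs". Section 4.8.6 removes subjects with wild-type RSV infection from the immunogenicity cohort.

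Existing firewall: where the sponsor must see unblinded data to decide on cohort progression or continued enrollment, Section 4.6.2 forbids those employees to deal directly with sites, disclose allocation or take part in evaluating subjects.

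**The concern.** Safety is the primary endpoint. Its late components depend on how events are queried, coded and classified over many months after the interim. Read as written, the protocol lets the sponsor staff who do that work know who received vaccine and who received placebo. Because the early safety data are unlocked and no dated data cut is required, a reader of the final report could not tell from the protocol's rules which Day 1 to 90 entries changed after unblinding.

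The protocol already has a suitable firewall for a narrower situation during enrollment. It drops it at the point where unblinding becomes much wider. At stake is the credibility of the long-term safety comparison with placebo and of the later immunogenicity summaries. Arms are small: with 20 subjects per active arm, one subject reclassified moves a proportion by 1/20 = 5 percentage points.

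**Working it through.** The protocol gives no figure to reproduce here, and no power or alpha calculation applies. The check compares sections and counts what is still open at unblinding. Days are nominal, ignoring visit windows.

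**1. Does any section keep part of the sponsor blinded?** Sections 4.6.2 and 4.6.3.2 refer to MedImmune staff and employees without a subset. Section 6.4 does not exempt Data Management. A general sentence in Section 4.6.2 says that sponsor staff involved in clinical evaluation are unaware of treatment, but it refers to Section 4.6.3.2 for the interim, so it does not limit the unblinding there. Section 9 describes the change to 4.6.2 as covering all MedImmune staff.

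**2. Does the firewall continue?** The rule in Section 4.6.2 is tied to cohort progression and continued enrollment. Both decisions are over once every subject has passed Day 91. Sponsor contact with sites is not over: Section 6.2 (monitoring), Section 5.7.2 (medical monitor reviews hepatic events with the investigator) and Section 5.5.2 (sponsor may request more on ongoing events).

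**3. Primary-endpoint components (Section 2.2.1).**
- Windows already closed: solicited symptoms to Day 7, AEs to Day 28, SAEs to Day 28. That is 3 of 6, closed but unlocked.
- Still accruing: SAEs, NOCDs and AESIs to Day 360. That is 3 of 6.

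**4. Safety follow-up remaining.**
- Last subject: 360 − 90 = 270 days; 270/360 = 75%. Of 15 scheduled post-dose contacts, 9 fall after Day 91.
- First subject in Cohort 1: there are three escalation steps (1 to 1a/2, to 2a/3, to 3a), each at least 3 days of staggering plus 7 days of follow-up (Sections 3.1.2 and 3.1.3), then 3 days of staggering in Cohort 3a. Minimum lead = 3 × (3 + 7) + 3 = 33 days. That subject is at Day 91 + 33 = 124 or later, leaving at most 361 − 124 = 237 days; 237/360 = 66%.

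**5. Antibody time points (Section 2.2.2): Days 29, 61, 91, 181, 271, 361.** After Day 91: 181, 271 and 361, so 3 of 6. This is exact for the last subject. At minimum staggering it also holds for the first (Day 124 is before Day 181). With slower enrollment, some early subjects will already have given later samples.

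**6. Triggers.** Section 4.6.3.2 requires only that all Day 91 visits are complete. Section 4.6.2 also requires cleaned and monitored Day 90 safety data and final Day 28 immunogenicity data. These are different dates.

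**The case against.** The strongest reply is that the people who create the data stay blinded. Subjects fill in the diary cards, site staff sign and date any update, and investigators assess severity, relationship and seriousness, answer queries and sign the eCRFs. The AESI list is largely closed, hepatic events have numeric thresholds, and anaphylaxis is analyzed by preferred term. Leaving the data unlocked has a stated and sensible purpose, since early events can surface at later contacts. An unblinding plan and a Data Management Plan exist and may restrict access. All analyses are descriptive.

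Much of this stands, and it rules out several stronger readings that a reader might infer:
- That unblinded staff can edit primary-endpoint data. The protocol gives them no such right; entries belong to blinded investigators.
- That the dose-selection dataset cannot be reproduced. Unlocked does not mean unarchived; the protocol simply requires no dated cut.
- That monitors will unblind sites. Section 6.2 speaks of a MedImmune representative, who need not be an employee, and the site-management CRO stays blinded.
- That five of six antibody time points are exposed. That assumes the Day 61 and 91 results are still outstanding, which no section says. The assay CRO also stays blinded.

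What the reply does not remove is the indirect route. Sponsor Data Management is not exempted. Some latitude remains in which MedDRA terms count as associated, and the protocol does not say who decides. The wild-type RSV exclusion is also applied to data still arriving. The unblinding plan may add detail, but the protocol's own wording grants full unblinding to employees with no named group.

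**Conclusion.** The point holds in a limited form. As written, the protocol lets sponsor staff who know the allocation raise queries, code events, classify AESIs and apply wild-type RSV exclusions, on Day 1 to 90 safety data that are not locked and on later data still to come. Three of six primary-endpoint components are still accruing, with up to 270 of 360 days left for the last subject and at most 237 for the first. Three of six antibody time points are not yet sampled for the last subject.

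The bias is possible and indirect; nothing here shows that it would occur or how large it would be. No type I error rate or decision threshold is affected. The conclusion assumes that the unseen unblinding plan does not already restrict access. If it does, the protocol wording should be brought into line with it. The two triggers differ in any case and need reconciling. This is a change the sponsor should make, not a defect that invalidates the study.

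**What to change.** - **Section 4.8.6:** before unblinding, archive a dated snapshot of the Day 1 to 90 safety and safety laboratory data. Enter every later change or late-learned event as a flagged, logged addition. A hard lock of early data is not needed and would fit poorly with the stated aim of capturing late reports.
- **Sections 4.6.2 and 4.6.3.2:** limit interim unblinding to a named analysis and dose-selection team. Keep data management, coding, AESI classification and site-facing staff blinded until the final lock. The emergency and regulatory-reporting provisions can stay as they are.
- **Section 4.6.2:** extend the existing bar on site contact and subject evaluation by unblinded sponsor employees past the interim, to the final lock.
- **Sections 4.6.2 and 4.6.3.2:** state one trigger for unblinding.

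The cost is protocol and unblinding-plan wording, an access list, and a small loss of convenience for sponsor staff outside the named team. No visits, samples or subjects are added.

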- The proportion of all subjects in the immunogenicity population who experience a post-dose cell-mediated immune response to RSV F on Days 8 and 29 as measured by the RSV F peptide pool IFN γ ELISPOT assay

Exploratory Endpoints

Depending on assay availability and the availability of suitable samples, the following exploratory endpoints may be assessed to further evaluate immune responses to RSV:

- The proportion of subjects who experience a post-dose seroresponse to RSV on Days 29, 61, 91, 181, 271, and 361 as measured by palivizumab-competitive enzyme-linked immunosorbent assay (cELISA), with seroresponse defined as ≥ 4 -fold rise from baseline
- Post-dose GMTs and GMFRs from baseline of palivizumab-competitive antibodies as measured by a palivizumab-cELISA on Days 29, 61, 91, 181, 271, and 361
- The proportion of subjects who experience a post-dose seroresponse to RSV on Days 29, 61, 91, 181, 271, and 361 as measured by neutralizing antibody to RSV B, with seroresponse defined as a ≥ 4 -fold rise from baseline
- Post-dose GMTs and GMFRs from baseline of RSV B neutralizing antibodies on Days 29, 61, 91, 181, 271, and 361
- The number of RSV F-specific CD8 $^+$ and CD4 $^+$ T cells that secrete interleukin 2 (IL-2), IFN γ , tumor necrosis factor alpha (TNF- α), interleukin-4 (IL-4), interleukin 5 (IL-5), and/or other cytokines prior to and post dosing in subjects who received MEDI7510. An exploratory intracellular cytokine flow cytometry assay may be used for these analyses.
- The types of cytokines (Th1 vs Th2 vs inflammatory) secreted by RSV F-specific T cells prior to and post dosing in subjects who received MEDI7510. An exploratory Luminex assay for Th1/Th2 cytokines may be used for these analyses.

STUDY DESIGN

This is a Phase 1a, first time in human (FTIH), double-blind, randomized, placebo-controlled, cohort escalation study evaluating the safety and tolerability of a single ascending IM dose of RSV sF or MEDI7510 in adults ≥ 60 years of age who are healthy or who have stable, chronic underlying medical conditions. Approximately 144 subjects will be enrolled at approximately 3 study centers in the United States and randomized in a 5:1 ratio by cohort to receive a single dose of either RSV sF or placebo or MEDI7510 or placebo on Day 1 in ascending doses as follows:

- Cohort 1: 20 μ g RSV sF (n = 20) or placebo (n = 4) as a single IM injection
- Cohort 1a: 20 μ g MEDI7510 (n = 20) or placebo (n = 4) as a single IM injection

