1 INTRODUCTION

1.1 Disease Background

Respiratory syncytial virus (RSV) is a significant cause of respiratory disease, including pneumonia, in adults as well as children. Symptomatic RSV re-infection occurs commonly throughout life. RSV outbreaks occur in a seasonal pattern that is similar, but not identical, to that of influenza, generally spanning the months of November to April in the Northern Hemisphere; however, unlike influenza, RSV re-infection is not dependent on seasonal antigenic variation and is thought to occur because of a short duration of immunity after infection ([Hall et al, 1991](#)). Most RSV infections are unrecognized in adults because respiratory samples are not routinely tested for RSV in this population. Recent epidemiologic data highlight the importance of RSV as a cause of respiratory illness in adults, including illness resulting in hospitalization and death, particularly in older adults or in those with underlying cardiac or pulmonary disease ([Falsey et al, 2005](#); [Walsh et al, 2004](#); [Widmer et al, 2012](#); [Mullooly et al, 2007](#)). Older adults are more likely than younger adults to have severe manifestations of RSV illness ([Mullooly et al, 2007](#); [Walsh et al, 2013](#); [Zhou et al, 2012](#)).

In a recently completed 4-season assessment of patients with polymerase chain reaction (PCR)-confirmed RSV-associated respiratory disease that resulted in medical provider contact, the estimated seasonal incidence of medically attended RSV disease was 1.6% per season in patients ≥ 50 years of age and 1.8% in patients ≥ 60 years of age (McClure et al, Marshfield Clinic, unpublished data). In another prospective study of healthy older adults ≥ 65 years of age followed for respiratory illness for 4 consecutive seasons, the incidence of RSV infection (not necessarily medically attended) diagnosed by culture, PCR, or serology was 3% to 7% annually ([Falsey et al, 2005](#)). Illness duration averaged 16 days, and one third sought medical care. In patients with high-risk conditions (chronic heart or lung disease), rates of RSV infection were 4% to 10% during the 4-year surveillance period; about half consulted a physician, 9% visited an emergency room, and 16% were hospitalized ([Falsey et al, 2005](#)).

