4.8 Statistical Evaluation

4.8.1 General Considerations

Tabular summaries will be presented by treatment arm within each dose cohort (Cohorts 1, 1a, 2, 2a, 3, and 3a) except that all placebo recipients will be grouped into a single placebo treatment arm, regardless of dose cohort. Categorical data will be summarized by the number and percentage of subjects in each category. Continuous variables will be summarized by descriptive statistics. Additional details of statistical analyses will be described in the statistical analysis plan.

The As-treated Population (ATP) includes all subjects who receive any amount of investigational product. Subjects will be included in the ATP according to the investigational product received even if different from that to which the subject was randomized.

All analyses will be performed on the ATP unless otherwise specified.

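### Section 4.8.6 drops whole subjects after wild-type RSV infection rather than only the samples taken after it; the effect is small, but valid Day 8 and Day 29 results can be lost

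*Protocol*

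**What the plan says.** The rule stands in Section 4.8.6 (Interim Analysis) of the protocol. There, "wild-type RSV infection will be detected by anti-Ga, anti-Gb, or anti-N IgG assays derived from the RSV-specific 4-plex MSD assay", and the stated purpose is "to exclude subjects who have had wild-type RSV infections from the immunogenicity cohort". The same section sets the timing ("One interim analysis is planned after all subjects have completed the 90 days post dose safety follow-up") and the use: "This interim analysis will provide safety and immunogenicity data needed to select an antigen dose to include in the Phase 1b study".

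Elsewhere:

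- Section 4.3.4.1 gives the detection method only.
- Section 4.8.1 sets the default: "All analyses will be performed on the ATP unless otherwise specified".
- The synopsis words one cellular endpoint as "The proportion of all subjects in the immunogenicity population who experience a post-dose cell-mediated immune response to RSV F on Days 8 and 29". The matching bullet in Section 2.2.2 does not mention that population, and the protocol does not define it.
- Section 4.8.7 (Final Analysis) neither repeats nor changes the infection rule.
- Section 2.2.2 places the humoral endpoints on Days 29, 61, 91, 181, 271 and 361, and the ELISPOT endpoints on Days 8 and 29.

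**The concern.** Removing samples taken after a natural infection is sound, because infection can itself raise anti-F, neutralising and T-cell readouts and so imitate a vaccine response. The difficulty is the unit of exclusion. An infection after Day 29 cannot have affected the Day 8 or Day 29 sample, yet the rule as worded takes the subject out.

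There are two consequences. Clean early data are lost. And the early estimates are restricted to subjects who later stayed uninfected, which is a post-randomisation condition. Section 1.2 says the immune responses being measured are thought to help prevent infection, and Section 1.5 says the vaccine is meant to prevent RSV disease. If that is right, the infected subjects are on average the weaker responders, and dropping them raises an arm's GMT, GMFR and seroresponse rate. These summaries feed the choice of antigen dose for Phase 1b.

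**Working it through.** The protocol gives no figure for the number excluded or the effect of exclusion, so there is nothing of its own to reproduce. The steps below size the effect.

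**Inputs from the protocol.** 20 active subjects per cohort and 144 in total (Section 3.1.2); infection in healthy older adults "diagnosed by culture, PCR, or serology was 3% to 7% annually" (Section 1.1); sampling days from Section 2.2.2; interim after 90 days.

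**Assumptions, not in the protocol.** Risk over the first 90 days is either one quarter of the year's risk (even spread) or one half of it (all risk in a 6-month season that contains the 90 days). Post-dose titre has SD 1.5 on the log2 scale. The odds of infection are multiplied by OR = 1 (no link), 0.7 or 0.5 for each two-fold higher titre.

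**Step 1: subjects excluded.** With annual rate r, the fraction infected is q = 1 − (1 − r)^f, where f = 0.25 (even) or 0.5 (season) for 90 days, and q = r for a year. The expected loss per arm is 20q, and the chance that an arm loses at least one subject is 1 − (1 − q)^20.

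**Step 2: selection effect.** Take x ~ N(0, 1.5²) and logit P(infected | x) = a + x·ln(OR), with a chosen so that the mean probability is q. The GMT among subjects kept is inflated by the factor 2^m, where m = E[x(1 − P)] / E[1 − P].

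| Rate and window | q | Lost per 20 | Lost per 144 | P(at least 1 of 20) | Inflation, OR 1 | OR 0.7 | OR 0.5 |
|---|---|---|---|---|---|---|---|
| 3%, 90 days, even | 0.0076 | 0.15 | 1.1 | 14% | 0 | 0.4% | 0.8% |
| 3%, 90 days, season | 0.0151 | 0.30 | 2.2 | 26% | 0 | 0.8% | 1.6% |
| 7%, 90 days, even | 0.0180 | 0.36 | 2.6 | 30% | 0 | 1.0% | 1.9% |
| 7%, 90 days, season | 0.0356 | 0.71 | 5.1 | 52% | 0 | 2.0% | 3.7% |
| 3%, full year | 0.03 | 0.6 | 4.3 | 46% | 0 | 1.7% | about 3% |
| 7%, full year | 0.07 | 1.4 | 10.1 | 77% | 0 | 3.9% | 7.2% |

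**Step 3: how often the early sample is clean.** If infection time is uniform over follow-up, the Day 29 sample predates infection in (91 − 29)/90 = 69% of those infected by Day 91, and in (361 − 29)/360 = 92% of those infected by Day 361. For Day 8 the shares are (91 − 8)/90 = 92% and (361 − 8)/360 = 98%. Exclusion by subject loses all of these.

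**Step 4: comparison with sampling error.** With SD 1.5, the standard error of an arm's mean log2 titre is 1.5/√20 = 0.335. The 95% interval for the GMT is then a factor of 2^(±2.093 × 0.335), or about 0.61 to 1.63. Losing one subject of 20 widens the standard error by √(20/19) = 1.026, or 2.6%.

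**The case against.** The strongest reply has five parts.

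*The SAP may narrow the rule.* Section 4.8.1 leaves analysis details to the SAP, which is not at hand, and Section 4.8.6 does not state which visits an infected subject loses. A reader might infer that every sample is certainly discarded. That is the plain reading, but the protocol does not say so expressly. What stands against the reply is that the only rule stated is by subject, and nothing in the protocol keeps earlier samples.

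*The interim may not see later infections.* Section 4.6.2 ties sponsor unblinding to final immunogenicity data through Day 28, and the infection markers come from the same 4-plex assay as anti-F IgG. If interim serology stops at the Day 29 sample, nobody is removed for a later infection. A subject positive at Day 29 has an affected Day 29 sample anyway, so the two rules differ only for Day 8 ELISPOT. This reading is possible but not certain.

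*The effect is small and partly shared.* A reader might take the full-year losses as the harm to dose selection. They are not: the rule sits in the Day 90 section, and the 90-day shifts are minor beside the sampling error in step 4. Similar shifts in the active arms would also partly cancel when doses are compared. This stands.

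*The bias needs a link between response and infection.* With no link it is zero and only precision is lost. Section 1.5.1 calls the possibility of benefit unknown. This stands too.

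*A sample-level rule does not remove all conditioning.* Visits after infection are still restricted to subjects not yet infected, and a sample taken after infection but before seroconversion may be kept. This is right, and it is why the fix includes an all-samples summary.

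**Conclusion.** The point holds as a modest fault in a stated rule. Exclusion by subject, with no limit to samples after infection, can discard valid Day 8 and Day 29 results and makes them conditional on a later event that vaccine response may change.

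At the interim the expected loss is about 0.15 to 0.7 subjects per 20-subject arm at 3% to 7% annual infection. GMT inflation is 0% to about 4%, and for Day 29 humoral results possibly nil if serology stops at Day 29. If the rule is carried to the final analysis, the loss is about 0.6 to 1.4 subjects per arm over a year with 0% to about 7% inflation. Day 29 tables could then differ from those used at the interim. The inflation figures rest on the assumed SD and odds ratios.

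The documents do not support the stronger conclusion that dose selection is materially distorted. Nor do they establish that the rule applies at the final analysis, since Section 4.8.7 is silent. The endpoints are secondary and descriptive. The change is still worth making, because a better rule uses data already collected.

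**What to change.** In Section 4.8.6, and explicitly for the final analysis in Section 4.8.7, replace the exclusion of subjects with: *Immunogenicity samples collected at or after the first sample showing serologic evidence of wild-type RSV infection are excluded; all earlier samples from that subject are retained.*

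Report the number of subjects and samples affected by arm and visit. Repeat the immunogenicity summaries on all as-treated samples, so that the reader can see what the exclusion does at visits where conditioning on infection remains. Use the same population wording for the cellular endpoint in the synopsis and in Section 2.2.2.

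The cost is a sentence in each place and one extra set of tables. No new data or assays are needed.
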